Pre-visit Questionnaire to Increase Influenza Vaccinations

Study Protocol with Statistical Analysis Plan

NCT05508698

7/21/2023

Study Protocol

Scientific Background

Almost everyone ages 6 months or older can benefit from the influenza vaccine, which can reduce illnesses, missed work, hospitalizations, and death by reducing the likelihood of contracting influenza.

Objectives

The purpose of this study is to assess, prospectively, the effect on flu vaccination rates of a pre-visit questionnaire that asks patients to indicate their preferences for a flu shot at an upcoming appointment. Responses to the questionnaire are shown to clinicians via additional text in an existing flu shot alert. The investigators hypothesize that the pre-visit questionnaire will lead to increased flu vaccination compared with standard practices.

Design

This study is a randomized controlled trial with 2 study arms. Patients were pre-randomized to receive (or not receive) a one-item, pre-visit questionnaire about the flu shot. Questionnaire responses are shown to clinicians in an existing flu shot alert.

Methods

Patients were pre-randomized to two study arms in July 2022:

1. Passive Control: No change to standard of care for flu vaccines
2. Pre-visit Questionnaire: One-item questionnaire in online patient portal and additional information in the flu shot alert.

(Note that patients new to Geisinger after pre-randomization are not included in the study.)

Patients are enrolled in the study if they have a flu-shot-eligible appointment scheduled 14 days or less prior to their appointment.

Appointments are flu-shot-eligible if the appointment department administers flu shots (according to an EHR classification list) at the time the appointment questionnaire becomes available (14 days prior to the appointment for appointments scheduled 14 days or more before the appointment, or on the day the appointment is scheduled for appointments scheduled less than 14 days in advance).

For those in the passive control arm, we will retrospectively identify flu-shot-eligible appointments based on the departments and date ranges observed in the questionnaire arm. For example, if questionnaires were sent to patients in the questionnaire arm for appointments in a given department from 9/1/22–12/31/22, an appointment in that same department in that date range will be considered flu-shot-eligible for a patient in the passive control group.

Additionally, patients are enrolled if, according to the EHR, they have not yet received a flu shot at the time the questionnaire becomes available (or at the time it would have become available for the passive control group).

Power Analysis

We expect that about 165,000 patients will be enrolled in the study (~82,500 per arm). This sample size allows 80% power to detect an increase in flu vaccination rates from 35% to 35.7% with two-tailed $\alpha = .05$ for any comparison between study arms.

Project Status

Patients were pre-randomized to their study arms in July 2022. Enrollment was complete on 4/1/23, after which the flu shot alerts were turned off across the system. Data collection continued until the primary outcome date of 4/8/23 (7 days after the final appointments). This updated version of the statistical analysis plan specifies slightly modified inclusion criteria for analysis, to correct as well as possible, and in an unbiased manner, for differences in how MyChart questionnaires were actually implemented relative to what was intended. No outcomes data were compared across study arms, and final outcomes data were not pulled or reviewed prior to uploading this document.

Statistical Analysis Plan

Planned Analyses

Primary Outcome: *Count of patients with a flu vaccination [Time Frame: Up to 21 days]*

Outcome Description: Patient received a flu vaccine (yes/no) between the day questionnaires became available for the patient's first scheduled flu-shot-eligible appointment and 7 days following the appointment. Questionnaires were available 14 days prior to the appointment date for appointments scheduled at least 14 days in advance. Questionnaires were available on the day the appointment was scheduled for appointments scheduled less than 14 days in advance.

Note that control patients did not receive a flu shot questionnaire, but they may have received other questionnaires from the health system 14 days before their appointment. We will conduct subgroup analyses for people who had responded to MyGeisinger pre-visit messages in the previous year and those who did not.

Question: Does a pre-visit questionnaire that allows patients to indicate their flu shot preferences increase the likelihood that they will get a flu shot?

Analysis (Confirmatory): We will test the hypothesis that a pre-visit flu-shot questionnaire increases the likelihood that patients will get a flu shot. We will run an OLS regression to examine whether flu vaccination differs as a function of experimental arm.

Analysis Notes

To identify the primary analysis sample, we will limit the dataset to the first flu shot-eligible appointment for which each enrolled patient was scheduled. We will then further limit the

dataset to appointments where patients were expected to receive a questionnaire (or for those in the passive control group, where the patient would have been expected to have received a questionnaire), as defined further here:

- The appointment was in a department and entailed an encounter type that was supposed to trigger a questionnaire (even if a questionnaire was not always triggered)
- The patient was not marked as contraindicated for the flu vaccine in the flu shot BPA for the 150 days prior to the questionnaire
- The patient had a “flu shot overdue” health maintenance topic (HMT) as of two days prior to the questionnaire launch date, ensuring sufficient time for the HMT to successfully trigger the questionnaire (given that a large proportion of questionnaires were not triggered when the HMT was too recent), OR the appointment was between 9/1/22 and 9/15/22, at which time the questionnaires were triggered regardless of the HMT status

Recent work suggests that OLS regressions are appropriate in randomized experiments with binary outcome variables such as ours (Gomila, 2021).

As the treatment variation is at the individual level, we will report heteroskedasticity-robust standard errors. We will also explore the impact of clustering these standard errors at the clinic and clinic-date levels to allow for dependence across observations within these clusters. We will also investigate heterogeneity across clinics that vary along characteristics of interest, including prior-year vaccination rates.

We may run additional robustness checks. These checks may include focusing on additional inclusion/exclusion criteria (e.g., including subsequent visits with questionnaires for a given patient) and subpopulations (e.g., different visit types).

Other Pre-specified Outcomes

Other Pre-specified Outcomes listed below include flu outcomes (diagnosis, complications) and COVID-19 vaccination. If there are any differences in these outcomes as a function of study arm, the mechanism would almost certainly be increased flu vaccination. Therefore, we will only run analyses on Other Pre-specified Outcomes for analyses above where there is a significant difference in flu vaccination.

1. Count of patients with a high confidence flu diagnosis

Patient received a flu diagnosis via a positive polymerase chain reaction (PCR)/antigen/molecular test (yes/no) during the 2022-23 flu season (from the patient’s study start date through April 30, 2023).

[Time Frame: Up to 8 months]

2. Count of patients with a "likely flu" diagnosis

Received a "high confidence flu" diagnosis (with positive PCR/antigen/molecular test) and/or "likely flu" diagnosis (as assessed via International Classification of Disease [ICD] codes or Tamiflu administration or positive PCR/antigen/molecular test) (yes/no) during the 2022-23 flu season (from the patient’s study start date through April 30, 2023).

Note that "likely flu" is a superset of the "high confidence flu" diagnoses.

[Time Frame: Up to 8 months]

3. Count of patients with flu complications

Diagnosed with flu-related complications (yes/no) from the patient's study start date through July 31, 2023.

[Time Frame: Up to 11 months]

4. ER visits

Number of ER visits from the patient's study start date through July 31, 2023.

[Time Frame: Up to 11 months]

5. Hospitalizations

Number of hospitalizations from the patient's study start date through July 31, 2023.

[Time Frame: Up to 11 months]

6. COVID-19 vaccination rates

Received at least one COVID-19 vaccination (yes/no) during the 2022-23 flu season (from the patient's study start date through April 30, 2023).

[Time Frame: Up to 8 months]

7. Count of patients with a flu vaccination during the 2022-2023 season

Patient received a flu vaccine (yes/no) during the 2022-23 flu season (from the patient's appointment date through April 30, 2023)

[Time Frame: Up to 8 months]

Additional Exploratory Analyses

1. Age and sex

People of different ages and sexes may react differently to the questionnaire. To test the relation between flu shots, age, and sex, we will run an OLS regression including binned patient age (18–24, 25–34, 35–44, 45–54, 65+), sex, and their interaction.

We will additionally test for an interaction between age, sex, and study arm, as people of different ages and sexes may be differentially receptive to different alert versions.

We may also test whether alert effectiveness varies by clinician age and/or sex.

2. Number of appointments with a flu shot questionnaire

Patients may have received more than one flu-shot questionnaire during the flu season. We will explore whether vaccination rates increased with more exposure to the flu-shot questionnaire in the experimental group compared with those in the control group who had the same number of eligible appointments but were not sent the questionnaire.

3. Appointment department/specialty

Some departments give more flu shots than others. We will test if alerts with or without questionnaire responses are differentially effective as a function of department or specialty, to see if some versions are particularly helpful for under-performing departments or specialties.

4. Contamination analysis

Although randomization was at the patient level, the alert portion of the intervention was directly experienced by clinicians rather than patients. Many clinicians encountered patients and their assigned alerts for both experimental arms. We will explore whether contamination was present in our data due to clinicians' exposure to multiple experimental conditions (e.g., by examining results as a function of clinic-level variation in the number of patients randomly assigned to each arm and/or as a function of the duration of exposure to the information).

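### Control appointments are made eligible by send ranges observed in the questionnaire arm, not by the EHR list, so inclusion and outcome window can depend on arm: a probably small bias and a cheap clarification

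*Combined protocol and SAP*

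**What the plan says.** The Methods section gives a general rule: an appointment is flu-shot-eligible "if the appointment department administers flu shots (according to an EHR classification list) at the time the appointment questionnaire becomes available". That day is 14 days before the visit, or the booking day for visits booked later than that.

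For the passive control arm the next paragraph gives a different rule: "we will retrospectively identify flu-shot-eligible appointments based on the departments and date ranges observed in the questionnaire arm". Its example makes the range depend on actual sending: "if questionnaires were sent to patients in the questionnaire arm for appointments in a given department" over a stated period, then a control appointment in that department and period counts as eligible.

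Enrolment also requires no flu shot on record when the questionnaire becomes available, "or at the time it would have become available for the passive control group".

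Under Project Status, the update is said to correct, as well as possible and "in an unbiased manner, for differences in how MyChart questionnaires were actually implemented relative to what was intended".

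The Analysis Notes fix the order of selection. The analysis will first "limit the dataset to the first flu shot-eligible appointment for which each enrolled patient was scheduled". The next sentence opens "We will then further limit the" and goes on to keep only appointments where a questionnaire was expected or, for controls, "where the patient would have been expected to have received a questionnaire". The department and encounter-type part of that restriction concerns intended triggering, whether or not a questionnaire actually went out.

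The primary outcome window runs from the availability day of the first eligible appointment to 7 days after that appointment.

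**The concern.** Randomisation protects the primary comparison if one rule, blind to arm, decides who is analysed and from which date. Here eligibility determines three things: whether a patient is in the sample, the date on which prior vaccination is checked, and the outcome window. If eligibility comes from a list in one arm and from observed sends in the other, all three can differ by arm for reasons unrelated to the questionnaire's effect.

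The matter deserves attention because the target effect is small (35% to 35.7%) and because the document itself reports that sending departed from intent.

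**Working it through.** **1. Where the two rules can disagree**

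| Situation | List rule | Send-range rule (controls) |
|---|---|---|
| Visit inside the range, some sends missed | Eligible | Eligible: no difference |
| Visit before the first or after the last observed send, department on the list | Eligible | Not eligible |
| Department's list status changed (none reported) | Judged on the availability date | Judged by visit date within the range |

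A hypothetical case for the third row: a department joins the list on 1 October. A visit on 5 October booked at least 14 days ahead has an availability date of 21 September, so it fails the list rule. If same-week bookings triggered questionnaires from 1 October, that visit lies inside the range and would count for a control.

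**2. Whether the later criteria repair this.** The first eligible appointment is chosen first and the Analysis Notes criteria are then applied. They can remove an appointment, but they cannot bring back a control appointment that the range rule left out, or return a patient to an earlier visit. The plan also does not say on which date intended triggering is judged, or from what source.

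**3. Scale for comparison.** From the Power Analysis: 82,500 per arm, 35% versus 35.7%, two-sided 0.05.
- Power at exactly 35.7% is 84.5%. At 80% power the detectable rate is 35.66%, which rounds to the stated 35.7%, so the plan's figure reproduces.
- Null SE = sqrt(2 × 0.35 × 0.65 / 82,500) = 0.00235, or 0.235 percentage points (pp). The 82,500 counts enrolled patients. Exclusions under the Analysis Notes make the SE larger, so the bias-to-SE ratios below are overstated if anything.

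**4. Simple bound.** If a share s of controls is dropped and their vaccination rate differs by g from those kept, bias = s/(1 - s) × g. With shift k = bias/SE, null rejection = Φ(-1.96 + k) + Φ(-1.96 - k). Both s and g are assumed.

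| s | g | Bias | k | Null rejection |
|---|---|---|---|---|
| 0.25% | 20 points | 0.05 pp | 0.21 | 5.5% |
| 1% | 10 points | 0.10 pp | 0.43 | 7.1% |
| 1% | 20 points | 0.20 pp | 0.86 | 13.8% |

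**5. Do the edges produce such gaps?** Two null simulations; every input beyond sample size is assumed.

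*Simple:* 165,000 appointments spread evenly over 213 days, 50 to 1,000 departments, 50% or 100% of questionnaires sent, vaccination falling from 50% to 20%. The range rule drops about 0.02% to 4.4% of control appointments but adds at most about 0.005 pp of bias, because early and late ends are trimmed about equally.

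*Fuller:* 165,000 patients, 212-day season, 1 + Poisson(1) appointments each, 300 or 900 departments of lognormal size, half of visits booked 14 or more days ahead, flu-shot-overdue topic active throughout in 60% and starting within 90 days in 40%, 15% vaccinated elsewhere. Vaccination falls from 55% to 11% (steep) or 40% to 30% (flat). Triggering is 90% or 100% on 9/1-9/15. After that it is 90% or 50% when the topic is old enough, and 20% or 10% respectively when it is too recent. The later criteria are applied after the first appointment, without re-selection.
- No list changes, 16 scenarios: -0.07 to +0.05 pp, with 0.2% to 1.5% of controls lost.
- 10% or 30% of departments changing status, intended triggering judged on the availability date, 16 scenarios: -0.03 to +0.05 pp.
- The same changes with that criterion undated, 16 scenarios: -0.16 to +0.05 pp. Fifteen are below 0.3 SE. The exception (30% of 300 departments joining between 9/15 and 10/31, steep season) gives 0.159/0.235 = 0.68 SE and null rejection of about 10%.

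In the first two sets all 32 scenarios are below 0.3 SE, with null rejection of 5.0% to 5.9%. Signs are questionnaire minus control. The sign reverses with the trigger rates: in the steep, 900-department case, +0.045 pp when triggering is 90% early and 90% later, and -0.067 pp when it is 100% early and 50% later.

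**The case against.** The strongest reply is that the plan already deals with most of this. The Analysis Notes criteria are worded for both arms, cover controls explicitly and rest on intended rather than actual sending. Questionnaires on 9/1-9/15 went out regardless of health-maintenance status, which limits trimming at the early edge. The simulated bias is below 0.3 SE in 47 of 48 scenarios, and the one exception needs widespread list changes that the document does not report. The two simulations also differ by more than tenfold, so the assumptions drive the answer.

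All of this stands, and it is why the point is minor. It does not remove the asymmetry, which is in the current text. The document does not say that the observed ranges also bind the questionnaire arm, that the list is applied to controls, or that the two rules will be compared.

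A reader might infer that every failed send carries over into control inclusion, since the document reports that many questionnaires were not triggered when the health-maintenance topic was too recent. That goes too far: a missed send inside a department's range changes nothing, and only the edges matter. A reader might also call the asymmetry simply avoidable. That is conditional, because the document does not say that a dated list can be recovered.

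**Conclusion.** The point holds as a minor one. Eligibility is defined differently for controls, and the order of selection means the later both-arm criteria limit the difference without removing it. Inclusion, index date and outcome window can therefore depend on arm.

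The document gives no number of departments, trigger rates, list history or count of affected appointments, so it fixes neither size nor sign. Under the stated assumptions and without list changes, the bias is at most about a tenth of the 0.7 pp target (0.07/0.7). A reader might conclude that the primary comparison is invalid, or that the update's aim of an unbiased correction has failed. Nothing in the document or in these calculations supports that. The larger values come from positing either a marked difference in the dropped controls or extensive list changes with an undated criterion.

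**What to change.** Before outcomes are compared across arms, determine department eligibility in both arms with one program that ignores arm and actual sends:

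1. Availability date = the later of (appointment date minus 14 days) and the scheduling date.
2. Judge the department from the dated EHR list, or the trigger configuration, on that date.
3. Take the patient's first such appointment and require no flu shot on record on that date.
4. Then apply all Analysis Notes criteria, including encounter type, in their existing order, as exclusions without re-selecting a later visit. Keeping encounter type at this stage leaves the intended population otherwise unchanged; moving it earlier is not needed for symmetry.

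State that the department and encounter-type criterion is judged on the availability date in both arms, and name its source. Keep the observed send ranges as a sensitivity analysis. Report index-appointment counts and dates by arm; counts alone could miss a shift in dates.

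**Cost:** SAP wording and one shared program, with no new patient data. The dated list must be retrievable, and the sample may change slightly. If the history cannot be recovered, apply the same observed ranges to both arms and state that some edge asymmetry remains, because the questionnaire arm defines the ranges. In the fuller simulation (900 departments, steep season, no list changes) this left +0.043 pp where the current rule gave +0.045, and +0.031 pp where it gave -0.067.

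Separately, the enrolment sentence in Methods limits enrolment to visits scheduled no more than 14 days ahead, while the eligibility paragraph and the outcome description include visits booked earlier. That conflict affects both arms alike and should be reconciled on its own.

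### The confirmatory endpoint measures vaccination in a window of at most 21 days, so it cannot by itself show a net gain over the season, and the planned season-long check starts on a different date

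*Combined protocol and SAP*

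**What the plan says.** Under Planned Analyses, the primary outcome is headed "Count of patients with a flu vaccination [Time Frame: Up to 21 days". It runs from questionnaire availability for the patient's "first scheduled flu-shot-eligible appointment and 7 days following the appointment". Availability is 14 days before the visit if it was booked at least that far ahead. Otherwise the window is shorter: "Questionnaires were available on the day the appointment was scheduled for appointments scheduled less than 14 days in advance".

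The aim is stated without any time limit in three places:
- Objectives: "the pre-visit questionnaire will lead to increased flu vaccination compared with standard practices".
- Planned Analyses, Question: whether the questionnaire will "increase the likelihood that they will get a flu shot".
- The hypothesis, as worded in the paragraph on the confirmatory analysis: "We will test the hypothesis that a pre-visit flu-shot questionnaire increases the likelihood that patients will get a flu shot".

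Season-long uptake is item 7 under Other Pre-specified Outcomes: "Count of patients with a flu vaccination during the 2022-2023 season", counted "from the patient's appointment date through April 30, 2023". The introduction to that section makes all the listed outcomes conditional on a significant difference in flu vaccination. Items 1 to 6 count from the patient's study start date. Only item 7 counts from the appointment date.

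**The concern.** Each patient's primary outcome closes 7 days after one appointment, while enrollment ran to 4/1/23 and the alerts stayed on until then. Controls keep standard care with the existing alert, and the plan expects some patients to have later eligible appointments. Take a patient who would have been vaccinated at a later visit but accepts at the first one because of the questionnaire. That patient counts as a success in the questionnaire arm, and the same patient in the control arm counts as a failure. By the end of the season both are vaccinated.

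A significant primary result could therefore be read as more people vaccinated when some or all of the difference is earlier vaccination. The plan neither discusses this nor limits the wording of the claim to the window. The outcome that could separate the two, item 7, has no stated link to the claim and does not cover the same start of follow-up as the primary.

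**Working it through.** **Inputs from the documents.** Power Analysis: about 82,500 per arm, 35% versus 35.7%, 80% power, two-sided alpha 0.05. The period to which the 35% refers is not given. Primary outcome: at most 14 + 7 = 21 days.

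**Assumptions, not in the documents.** The share of controls vaccinated after the window (5%, 10%, 20%); control season-long rates of 35% to 60%; the share of any window gain that is only timing.

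**1. The plan's own figure.** Two-proportion normal approximation, with pooled variance under the null. At 82,500 per arm, 80% power is reached for a difference of 0.659 points (35% to 35.66%), which rounds to the stated 35.7%. A difference of 0.66 points needs 82,337 per arm. The figure is reproduced. For exactly 0.70 points:
- SE = √[(0.35×0.65 + 0.357×0.643)/82,500] = 0.00235
- 0.007/SE = 2.97, and 2.97 − 1.96 = 1.01, so power is 84.5%.

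**2. How much displacement would mimic the planned effect.** Let L be the share of controls vaccinated after the window. If a fraction f of those shots is brought into the window and nothing else changes, the window difference is f × L and the season-long difference is zero. Setting f × L = 0.007:
- L = 5%: f = 0.007/0.05 = 14%
- L = 10%: f = 0.007/0.10 = 7%
- L = 20%: f = 0.007/0.20 = 3.5%

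In each case the primary test is significant with 84.5% probability, while a correctly defined season-long test would be significant only at its 5% error rate.

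**3. What a season-long comparison can detect.** With 82,500 per arm and control season rates of 35% to 60%, the detectable difference at 80% power is 0.66 to 0.69 points. If the window gain is 0.7 points and a share of it is only timing, the season-long difference is 0.7 × (1 − share):

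| Share that is timing | Season-long difference (points) | Season-long power |
|---|---|---|
| 0% | 0.70 | 81–85% |
| 25% | 0.525 | 57–61% |
| 50% | 0.35 | 30–32% |
| 75% | 0.175 | about 11% |
| 100% | 0 | 5% (alpha only) |

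These figures use the expected enrollment. The SAP's further limits on the analysis sample could make it smaller.

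**4. Item 7 as worded.** Side by side:
- Primary: questionnaire availability to appointment + 7 days.
- Item 7: appointment to April 30, 2023.

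Read literally, a shot given after the questionnaire opens but before the appointment is a success for the primary and not for item 7. Suppose the questionnaire moves 0.35 points of shots from after the appointment to before it, with no net change over the season. Item 7 would then show a difference of −0.35 points. With control rates of 35% to 50%, that false deficit would reach significance with probability of about 30–32%. If instead the questionnaire produces genuinely additional shots before the appointment, item 7 would leave them out and understate the net gain.

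**The case against.** The endpoint can be defended. The intervention asks about a flu shot at a particular coming visit, so a window around that visit measures its direct effect. The time frame is openly labelled, the contrast is randomized, and earlier vaccination may have value in itself. All of that stands, and it is why the primary endpoint should stay.

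The plan also has a partial check. Item 7 is pre-specified, and the condition on the other outcomes triggers it exactly when the primary is significant. That stands too. What remains is its lower status, its absence when the primary is not significant, and its start date.

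A reader might infer more than the documents support:
- *That the plan already concludes more people are vaccinated.* It states a question and a hypothesis, contains no rule for the conclusion, and says that outcomes had not been compared across arms.
- *That a positive result would probably be timing.* The documents give no rate of vaccination after the window and no distribution of first-appointment dates, so it cannot be said that most windows close early in the season.
- *That the window must overstate the season-long effect.* Additional Exploratory Analyses, item 2, notes that patients may have received more than one questionnaire. Later exposure could make the season-long effect larger than the window effect.

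**Conclusion.** The point holds as a limit on interpretation, not as a fault in the primary test. A positive primary result supports a claim about vaccination by 7 days after the first eligible appointment. It does not by itself support a claim of net increase, which the untimed hypothesis invites. Item 7 as worded cannot cleanly settle the matter, because it drops shots that the primary counts.

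Neither the size nor the direction of the gap between window and season-long effects can be found in the documents. The 14%, 7% and 3.5% figures rest on assumed later uptake and show that full displacement is arithmetically possible, not that it is likely. The start-date mismatch does not depend on those assumptions, but its effect on the estimate depends on how many shots fall before the appointment, which is also not given.

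**What to change.** 1. Keep the primary endpoint and test. Word the conclusion as vaccination by 7 days after the first eligible appointment.
2. Redefine item 7 to run from questionnaire availability, or the equivalent date for controls, through April 30, 2023.
3. Make it the key secondary outcome in the same primary analysis sample, exempt from the condition on the other outcomes. Report its estimate and 95% CI beside the primary whatever the primary shows.
4. Base any statement about net or season-long increase on that estimate; otherwise state that a net gain was not shown. Do not make season-long significance a condition of the primary claim: with half of a 0.7-point gain being timing, that hurdle would be passed only about 30–32% of the time despite a real net gain of 0.35 points.

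**Cost.** SAP wording. The added days at the start of item 7 are already covered by the primary outcome, and its end date is unchanged. The SAP states that final outcome data had not been pulled or reviewed, so at that version the change could be pre-specified. The headline claim becomes narrower, and the season-long comparison will often be inconclusive if part of the window gain is only timing.

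### The confirmatory model is OLS on arm alone; a short list of covariates fixed before randomisation would add precision at little cost

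*Combined protocol and SAP*

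**What the plan says.** Under Planned Analyses, the confirmatory analysis is one sentence: "We will run an OLS regression to examine whether flu vaccination differs as a function of experimental arm". No covariate is named there. The Analysis Notes add heteroskedasticity-robust standard errors, with clustered versions as exploration.

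Patient characteristics appear only elsewhere in the plan:

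- The primary outcome section promises "subgroup analyses for people who had responded to MyGeisinger pre-visit messages in the previous year" and for non-responders.
- Additional Exploratory Analyses, item 1, states: "To test the relation between flu shots, age, and sex, we will run an OLS regression including binned patient age". It adds sex and the age-by-sex interaction, then an exploratory interaction of age, sex and arm.
- The Analysis Notes use clinic prior-year vaccination rates only to study heterogeneity between clinics.

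The optional robustness checks do not list covariate adjustment: "These checks may include focusing on additional inclusion/exclusion criteria" and subpopulations are the examples given.

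Project Status says that this version "specifies slightly modified inclusion criteria for analysis". The only sample size in the documents is the 165,000 patients expected to enrol (Power Analysis). No expected number is given for the restricted analysis set.

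**The concern.** The design difference is 0.7 percentage points, about three standard errors at the planned size, so modest changes in precision move power visibly. The plan already holds patient variables that it evidently expects to relate to vaccination, but it does not use them in the one test that counts.

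Two features of the plan raise the stakes. First, the primary sample is now restricted by department and encounter type, contraindication, and the timing of the overdue-vaccine flag (the health maintenance topic, HMT). The reason given for the timing rule is that "a large proportion of questionnaires were not triggered when the HMT was too recent". How many patients these rules remove is not stated. Second, the Other Pre-specified Outcomes are analysed only where flu vaccination differs significantly, so a missed primary result also closes off those analyses.

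**Working it through.** **Inputs from the Power Analysis section.** Control rate p0 = 0.35, questionnaire rate p1 = 0.357, two-sided alpha 0.05, target power 80%, about 82,500 per arm (equal allocation).

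**Assumed inputs.** The documents give neither the share of outcome variance explained by covariates (R²) nor the share of patients retained. Both are shown as ranges.

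**Step 1: reproduce the plan's figure.** Sum of variances: 0.35 × 0.65 + 0.357 × 0.643 = 0.2275 + 0.2296 = 0.4571. SE = √(0.4571 / 82,500) = 0.235 points. For exactly 0.7 points, z = 0.7 / 0.2354 = 2.974, and power = Φ(2.974 − 1.960) = 84.5%. The difference detectable with 80% power is 0.659 points, that is 35.66%, which rounds to the stated 35.7%. The plan's figure stands and is slightly conservative.

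**Step 2: adjusted model.** For main-effect covariates fixed before randomisation, SE ≈ √(0.4571 × (1 − R²) / n). The n per arm for 80% power is (1.960 + 0.842)² × 0.4571 × (1 − R²) / 0.007².

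| Assumed R² | SE at 82,500 (points) | Power at 82,500 per arm | Power at 66,000 per arm (80% retained, assumed) | n per arm for 80% power | As share of 82,500 |
|---|---|---|---|---|---|
| 0 (arm only) | 0.235 | 84.5% | 75.8% | 73,211 | 88.7% |
| 0.02 | 0.233 | 85.2% | 76.6% | 71,747 | 87.0% |
| 0.05 | 0.229 | 86.2% | 77.9% | 69,551 | 84.3% |
| 0.10 | 0.223 | 88.0% | 80.1% | 65,890 | 79.9% |
| 0.20 | 0.211 | 91.4% | 84.5% | 58,569 | 71.0% |

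The equivalent gain in sample size is 1/(1 − R²) − 1: about 2%, 5%, 11% and 25% for the four adjusted rows.

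**Step 3: what these R² values require.** For one covariate split 50/50, the vaccination gap needed is √(R² × 0.2275 / 0.25). This gives about 13, 21, 30 and 43 points for R² of 0.02, 0.05, 0.10 and 0.20. Age, sex and portal response alone may therefore sit near the top of the table.

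**Step 4: check that adjustment does no harm.** In a simulation of 200 trials of 165,000 patients, one 50/50 baseline covariate had a 40-point gap (R² = 0.25 × 0.40² / (0.3535 × 0.6465) ≈ 0.175) and the true effect was 0.7 points. The mean robust SE fell from 0.235 to 0.214 points, as the formula predicts. Mean estimates were 0.693 points (arm only) and 0.689 points (adjusted), both close to 0.7.

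**The case against.** The strongest reply is that nothing is broken. An unadjusted risk difference in a patient-randomised trial is a valid and transparent confirmatory choice, and it exceeds its stated power at the planned size. That stands, and this point does not claim otherwise.

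The second reply is that the likely gain is small. At R² = 0.02, power rises by 0.7 points, and the retention needed for 80% power moves only from 88.7% to 87.0%. If 80% were retained, even R² = 0.05 would leave power at 77.9%. The larger gains probably need the patient's own prior-season vaccination, which the plan does not mention. This also stands and limits the benefit to be expected from the variables already planned.

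Third, the loss of patients is unknown. The plan calls the change slight, and its remark about untriggered questionnaires concerns recent flags, not the share of the analysis set removed. That is correct: the retention figures are thresholds, not forecasts.

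Fourth, the exploratory age, sex and arm model already puts these variables in one regression with arm. It is an interaction model, labelled exploratory, and does not adjust the confirmatory test.

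Finally, the document is dated 7/21/2023, after follow-up for the primary outcome ended on 4/8/23, and changing the confirmatory model late adds analyst discretion. That is a real constraint. The documents say that "final outcomes data were not pulled or reviewed prior to uploading this document", but they cannot show that this is still so. The recommendation is therefore conditional.

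**Conclusion.** The point holds as an efficiency improvement, not as a correction of an error. The confirmatory model uses arm alone although suitable patient-level covariates are already in the plan. Adjusting for values fixed before July 2022 keeps the risk-difference estimand and, with equal allocation at this sample size, should not raise the standard error.

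At the planned size the gain is about 1 to 2 points of power for R² of 0.02 to 0.05, 3.5 points for 0.10 and 6.9 points for 0.20. It could decide whether 80% power is kept if the restricted set falls below about 88.7% of plan; at R² = 0.10 that threshold drops to about 79.9%. All of this rests on assumed R² and retention. If retention is near 100% and only age, sex and portal response are available, the benefit may be small.

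**What to change.** If outcomes are still unseen, define the confirmatory model as OLS of vaccination on arm plus these main effects, all set before randomisation:

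- age, continuous or in complete bins (the printed exploratory bins have nothing for 55–64);
- sex;
- response to portal messages in the year ending at the July 2022 randomisation (the plan gives its look-back year no anchor date);
- the patient's own prior-season flu vaccination, only if the EHR extract holds it.

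Keep the heteroskedasticity-robust standard errors and report arm-only OLS as a sensitivity analysis.

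Do not add department, clinic prior-year rate, scheduling lead time or calendar week without a stated justification that they are fixed before the questionnaire opens and unaffected by arm. Control eligibility is itself reconstructed: "we will retrospectively identify flu-shot-eligible appointments based on the departments and date ranges observed in the questionnaire arm".

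If outcomes have been seen, leave the confirmatory model as it is and report the adjusted model as supplementary.

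The cost is a short SAP paragraph naming the covariates, their coding and their cut-off date. Three of the four variables are already planned for analysis, although portal response must be anchored and the age bins repaired. Prior-season vaccination needs a check of the extract.
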